8.4 Analysis Population

8.4.1 Enrolled Population

The enrolled population comprises all patients who meet the eligibility criteria and are registered onto the study.

8.4.2 Safety Population

The safety population comprises all patients who have received at least one dose of the study medication. This set will be used for safety analysis.

8.4.3 Efficacy Population

The efficacy population comprises all patients who have received at least one dose of the study medication, have been evaluated for the primary endpoint, and have no significant protocol violations. This population will be used for efficacy analysis.

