3.6 Withdrawals

Subjects may discontinue study treatment or withdraw their consent to participate in the study at any time without prejudice. The investigator may withdraw a subject from study treatment or from the study if, in his or her clinical judgment, it is in the best interest of the subject or if the subject cannot comply with the protocol.

In addition, any of the following conditions require discontinuation of the subject from study treatment:

- An adverse event or intercurrent illness that in the opinion of the investigator warrants the subject's withdrawal from study treatment;
- The investigator believes it is not in the best interest of the subject to continue on study
- Specific conditions described in the Sections 4.4 Warnings and Precautions and Guidelines for the Management of Adverse Events;
- Necessity for treatment with other anticancer treatment prohibited by protocol;
- Sexually active subjects who refuse to use medically accepted barrier methods of contraception (e.g., male condom, female condom) during the course of the study and for 4 months after discontinuation of study treatment;
- Women who become pregnant or are breastfeeding;

CONFIDENTIAL

- If the subject does not recover from his or her toxicities to tolerable Grade ≤ 2 within 6 weeks, the subject will have study treatment discontinued unless there is unequivocal evidence that the subject is benefitting. In this situation, a subject may be able to restart therapy with a dose reduction upon resolution of the toxicity and with agreement of the sponsor-investigator;
- Request by regulatory agencies for termination of treatment of an individual subject or all subjects under the protocol;
- Significant noncompliance with the protocol schedule in the opinion of the investigator;
- Progressive disease (PD) or the subject no longer experiences clinical benefit as determined by the investigator

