| Contrast enhanced CT or MRI ⁶ | X | | | | | | X (every 8 weeks) | | |
| Archival Tissue Collection/Correlative Studies | | | | | | | | | |
| Blood sample collection ⁸ | | | X ¹⁰ | X | X | | X | | |
| Tissue sample collection ⁸ | X ⁷ | | | | | | | | |

CONFIDENTIAL

Footnotes:

1. Follow-up may be done by medical record review or phone call to subject and/or next of kin.
2. Subjects will be monitored for adverse events (AEs) from the time of first study intervention (i.e., biopsy, if needed, or treatment, whichever comes first).
3. Additional follow-up will occur for subjects with AEs related to study treatment that are ongoing at the time of this visit, and for subjects with SAEs related to study treatment that occur after the time of this visit.
4. A Full physical exam will be done in the pre-treatment period and on Cycle 1/Day 1. Physical exams may also be done by the investigator or qualified designee throughout participation in the trial as clinically indicated.
5. Vital signs include: height (at screening only), weight, temperature, pulse, respiratory rate, and blood pressure.
6. All sites of known disease must be assessed.
7. Patients will be asked for archival tissue during the screening period. Archival tissue is required pre-treatment as part of study eligibility to test for EGFR and c-MET expression. KRAS will also be tested if previous KRAS testing was not done or results are unknown AND there is adequate tissue available from tissue collected at screening
8. Only samples collected from eligible patients during the screening period will be utilized for the correlative studies which are outlined in this trial. Samples collected from ineligible patients during screening will be discarded.
9. Only for women of childbearing potential.
10. This sample may be collected any time after enrollment so long as it occurs before the patient takes his/her first dose of study medication on Cycle 1/Day 1.
11. The window for this test is within 28 days of starting treatment.

CONFIDENTIAL

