6.3.1.8 Disease Assessment

Contrast enhanced imaging studies (CT or MRI) will be performed at screening and every 8 weeks beginning Cycle 3/Day 1. All sites of known disease must be assessed. CT modalities should be done according to standard of care for the subject's disease.

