6.4 Post-Treatment Period

6.4.1.1 Safety Follow-Up

Subjects will return to the study site 30 to 37 days after their last dose of study drugs to complete end-of-study safety assessments.

Laboratory and physical examinations will be performed. Remaining study treatment will be returned by the subject, and treatment compliance via subject drug diaries will be documented. Additional follow-up will occur for subjects with AEs related to study treatment that are ongoing at the time of this visit, and for subjects with SAEs related to study treatment that occur after the time of this visit.

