8.3 Definition of Endpoints

Objective response (radiographic response) rate: proportion of all subjects with confirmed PR or CR according to RECIST 1.1, from the start of treatment until disease progression/recurrence

CONFIDENTIAL

(taking as reference for progressive disease the smallest measurements recorded since the start of treatment)

Disease control rate: proportion of all subjects with stable disease (SD) for 8 weeks, or partial response (PR), or complete response (CR) according to RECIST 1.1, from the start of treatment until disease progression/recurrence (taking as reference for progressive disease the smallest measurements recorded since the start of treatment).

Progression-free survival: a measurement from the date of first treatment until the criteria for disease progression is met as defined by RECIST 1.1 or death occurs. Subjects who have not progressed will be right-censored at the date of the last disease evaluation.

Overall survival (OS): a measurement from the date of first treatment until death from any cause.

Safety: Adverse event terms recorded in the eCRFs defined by the National Cancer Institute (NCI) CTCAE v4.03. Seriousness, severity grade and relationship to study treatment will be assessed by the investigator.

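### Section 8.4.3 can leave treated patients who die or stop before any on-treatment scan out of OS and PFS, and out of the ORR and DCR denominators that 8.3 defines over all subjects

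*Combined protocol and SAP*

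**What the plan says.** Section 8.4.3 admits to the efficacy population only patients who took at least one dose, "have been evaluated for the primary endpoint, and have no significant protocol violations", and assigns that population to the efficacy analysis. Section 8.9, headed Efficacy Analysis, covers ORR, DCR, PFS and OS and makes no exception for OS. The all-treated set in 8.4.2 is assigned to safety, and the enrolled set is used for baseline tables (8.6). No other section assigns a population to efficacy.

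Section 8.3 defines the endpoints differently. ORR is the "proportion of all subjects with confirmed PR or CR according to RECIST 1.1", and DCR has the same denominator. PFS runs from first treatment "until the criteria for disease progression is met as defined by RECIST 1.1 or death occurs". OS is "a measurement from the date of first treatment until death from any cause".

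The schedule shows how a treated patient can go unevaluated:

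- Imaging "will be performed at screening and every 8 weeks beginning Cycle 3/Day 1" (6.3.1.8).
- Section 3.6 ends treatment on progressive disease, or if "the subject no longer experiences clinical benefit as determined by the investigator".
- At the visit 30 to 37 days after the last dose, "Laboratory and physical examinations will be performed" (6.4.1.1). The imaging row of the table in 6.1 has no post-treatment entry.

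Survival is followed every 3 months for up to 2 years after treatment stops (6.5). Section 8.1 rules out imputation of missing data. Section 8.5 allows up to 40 enrolled because a few may not be evaluable for efficacy. Section 8.7 illustrates significant violations by example only.

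**The concern.** Patients with no response evaluation are likely to include those who do worst: early deaths, rapid deterioration and early stops. None of them can have a confirmed response, so dropping them can only raise ORR. Dropping early deaths lengthens PFS and OS. In a single-arm trial judged against a fixed rate, no control arm suffers the same loss and offsets it.

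The OS loss is the hardest to defend. OS needs no scan and the trial collects it, yet 8.4.3 makes membership of the OS analysis depend on a response evaluation.

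The second filter, significant violations, has no fixed direction of bias. But neither that term nor what counts as being evaluated is defined, so in an open-label trial membership can be settled after response is known.

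**Working it through.** **1. Route out of the analysis.** Cycles last 28 days (6.1), so Cycle 3/Day 1 falls after 2 × 28 = 56 days, about week 8. Take a patient who is dosed, deteriorates, stops at week 4 under 3.6 and dies at week 7 without an unscheduled scan. Under 8.3 this patient is a PFS event, an OS event and a subject without a response. Under 8.4.3 the patient was never evaluated for the primary endpoint, so is outside the set used for 8.9. The two sections give opposite answers and nothing reconciles them.

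**2. The plan's own design figures.** Inputs from 8.5: n1 = 11, stop if 0 respond; N = 37, reject the combination if 2 or fewer respond; null 0.025, alternative 0.150.

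- Early stop under the null: 0.975^11 = 0.757.
- Expected size: 11 + (1 − 0.757) × 26 = 17.32.
- P(positive) = Σ over x ≥ 1 of P(X1 = x) × P(X2 ≥ 3 − x), with X1 ~ Bin(11, p) and X2 ~ Bin(26, p).
- At p = 0.025: 0.2135 × 0.1371 + 0.0274 × 0.4823 + 0.0022 = 0.0447 (stated 0.045).
- At p = 0.150: 0.802 (stated type II error 0.198).

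The design reproduces exactly.

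**3. ORR.** The allowance in 8.5 is 40 − 37 = 3 patients. If 3 treated, unevaluated patients are dropped, ORR is multiplied by 40/37 = 1.08: 6/40 = 15.0% becomes 6/37 = 16.2%.

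**4. Type I error.** Assumption, not in the plan: the 2.5% null refers to all treated patients, 37 evaluable patients are reached, and the k excluded are non-responders. The rate among evaluable patients is then 0.025 × (37 + k)/37. The last column instead fixes the stage in which the exclusions fall, using n1 = 11 + k1 and N = 37 + k at p = 0.025, where k1 is the number excluded in stage 1.

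| k excluded | Evaluable rate | Type I error | Range (all in stage 2 to all in stage 1) |
|---|---|---|---|
| 0 | 0.0250 | 0.0447 | – |
| 1 | 0.0257 | 0.0477 | 0.0469–0.0495 |
| 2 | 0.0264 | 0.0507 | 0.0491–0.0544 |
| 3 | 0.0270 | 0.0539 | 0.0513–0.0594 |

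If the null refers to evaluable patients, or exclusion is unrelated to response, the figure stays 0.0447.

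**5. Median PFS or OS.** Assumption: times are exponential and the excluded share f is the earliest events. An exponential estimate of the median is multiplied by 1 − ln(1 − f). The sample median is multiplied by ln(0.5(1 − f))/ln 0.5.

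- f = 3/40: 1.078 and 1.112, so about 8–11%.
- f = 3/14 (a stage 1 stop with 11 evaluable and 3 excluded, an illustrative count): 1.241 and 1.348, so about 24–35%. Under the null the trial stops at stage 1 with probability 0.757.

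**6. Power if the 11 and 37 count treated patients.** If the 15% alternative refers to treated patients, power is 0.802. If it was meant for evaluable patients and a share f cannot be evaluated, the treated rate is 0.15 × (1 − f). Power is then 0.790, 0.778 or 0.764 at f = 2.5%, 5% or 7.5%.

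**The case against.** For ORR and DCR, 8.3 taken literally already keeps every subject in the denominator, and a subject without a confirmed response simply does not enter the numerator. The no-imputation sentence in 8.1 does not contradict that, because counting such a patient as a failure is an endpoint definition. This stands in part: for ORR and DCR the defect is an unreconciled conflict, and a reader who infers that 8.4.3 certainly removes these patients goes further than the text. It does not help OS or PFS, where 8.4.3 is the only rule on who is analysed.

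A reader might also infer that the stated 0.045 error rate is wrong. The documents do not support that. Section 8.5 expects non-evaluable patients and over-enrols for them, so the 2.5% null may well refer to evaluable patients, and then nothing is inflated. Even on the other reading, one exclusion stays below the 0.050 target. An evaluable set with an enrolment allowance is a recognised design choice for a response endpoint.

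Other limits also stand. Section 6 permits extra assessments when clinically indicated, and an early scan showing progression would keep a patient in. ECOG 0 or 1 and a life expectancy of at least 12 weeks (5.1) reduce early losses without excluding them. Deviations are logged within 5 days of discovery and reviewed monthly (9.7), and the cancer center judges their effect on data integrity (11.2). These controls limit late discretion but do not define which violations remove a patient from the analysis.

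**Conclusion.** The point holds as a conflict between sections and an avoidable exclusion. Under 8.4.3 and 8.9 as written, treated patients who die or stop unscanned can be left out of OS and PFS, and can leave the ORR and DCR denominators against 8.3. Loss of such patients favours the drug.

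Confidence is high on the text and low on the size, because the documents do not say how many patients will go unevaluated. At 3 of 40 the effect on ORR is 15.0% against 16.2%. Type I error is about 0.054 (0.051–0.059 by stage) only if the null refers to all treated patients. The 8–11% effect on the median should not be read as a ceiling: it assumes that 37 evaluable patients are reached and that the 3 earliest events are the ones lost, and 3 of 14 at a stage 1 stop gives about 24–35%. The case for change rests on OS, PFS and the conflict with 8.3, not on the error rate. This should be fixed, but it does not undermine the planned sample size.

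**What to change.** 1. **Sections 8.4.3 and 8.9:** analyse OS and PFS in all treated patients (the 8.4.2 set), with deaths before any scan counted as events. State how patients alive with no scan are handled for PFS, and report their number: censoring them on day 1 adds neither time nor an event to an exponential estimate, so it equals exclusion.
2. **Sections 8.3 and 8.4.3:** report ORR and DCR in all treated patients. Count those without a post-baseline evaluation as non-responders and not disease-controlled.
3. **Sensitivity analysis:** keep the evaluable, no-violation set. Define what counts as evaluated and which violations are significant before responses are reviewed.
4. **Sections 8.5 and 8.11:** state whether the 11 and 37 are treated or evaluable patients. This is partly a design choice. If treated, type I error stays 0.0447, and power is 0.802, or 0.790–0.764 under the evaluable reading in step 6 of the working. If 38, 39 or 40 treated patients are counted under the unchanged rule of 2 or fewer, with the extra patients in stage 2, type I error is 0.0469, 0.0491 or 0.0513 and should be reported.

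The cost is wording; no new data are needed, since survival is already followed. Reported rates may be slightly lower, and the stated power may need restating.

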8.5 Sample Size, Accrual and Study Duration

The optimal two-stage design to test the null hypothesis that $P \leq 0.025$ versus the alternative that $P \geq 0.150$ has an expected sample size of 17.32 and a probability of early termination of 0.757. If the drug is actually not effective, there is a 0.045 probability of concluding that it is (the target for this value was 0.050). If the drug is actually effective, there is a 0.198 probability of

CONFIDENTIAL

concluding that it is not (the target for this value was 0.200). After testing the drug on 11 patients in the first stage, the trial will be terminated if 0 respond. If the trial goes on to the second stage, a total of 37 patients will be studied. If the total number responding is less than or equal to 2, the combination is rejected. To allow for a few patients being not evaluable for efficacy, up to 40 subjects may be enrolled. It is estimated that two patients per month will meet eligibility criteria. As such we estimate 6 months to complete the first cohort and 15 months to complete enrollment to the second cohort. Average follow-up is expected to be 9 months to a year.

8.6 Patient Characteristics

Baseline patient characteristics will be tabulated in the enrolled population, such as demographics (age, race, gender), and disease characteristics (tumor location, stage).

8.7 Significant Protocol Violations

Significant protocol violations such as with respect to eligibility criteria and treatment plan will be tabulated.

8.8 Safety Analysis

The safety population will be used for all safety analysis. All safety data will be listed. For the treatment-emergent AEs, namely AEs started or worsened during the on-treatment period, the incidence will be summarized by system organ class and/or preferred term, severity based on CTCAE grades, type of adverse event and the relation to the study drug. Deaths reportable as SAEs and non-fatal serious adverse events will be listed by patient and tabulated by type of adverse event.

8.9 Efficacy Analysis

An exact binomial test will be used to test the hypothesis that radiographic response (ORR) is greater than 15%). ORR and DCR will be estimated with 95% exact binomial confidence intervals. Median PFS and OS will be estimated using 95% confidence intervals based on the exponential distribution. Safety and tolerability data will be tabulated.

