3 STUDY OBJECTIVES AND DESIGN

3.1 Study Objectives

3.1.1 Primary Objective

The primary objective of this trial is to demonstrate a radiographic response rate of 15% or greater for the combination in a selected population.

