8.11 Interim Analysis/Criteria for Stopping Study

After testing the drug on 11 patients in the first stage, the trial will be terminated if 0 respond. If the trial goes on to the second stage, a total of 37 patients will be studied. If the total number responding is less than or equal to 2, the combination is rejected.

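### Section 8.9 tests response against 15%, the design's target rate, instead of its 2.5% null; at a true 15% rate the stated test fails about 96% of the time

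*Combined protocol and SAP*

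**What the plan says.** The design is set out in Section 8.5 and repeated in the synopsis. It tests a null response rate of at most 0.025 against an alternative of at least 0.150 and "has an expected sample size of 17.32 and a probability of early termination of 0.757". For an ineffective drug, "there is a 0.045 probability of concluding that it is (the target for this value was 0.050"). The type II error at 15% is given as 0.198.

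The decision rule appears in the synopsis and in Sections 8.5 and 8.11. At the interim, "After testing the drug on 11 patients in the first stage, the trial will be terminated if 0 respond". At 37 patients, "If the total number responding is less than or equal to 2, the combination is rejected". Three or more responses is therefore a positive result.

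Section 8.9 is the section on how efficacy will be analysed. It says "An exact binomial test will be used to test the hypothesis that radiographic response (ORR) is greater than 15" per cent. It does not mention 2.5%, the two-stage rule, a significance level or sidedness. Section 8.3 treats objective response and radiographic response as one endpoint, so both tests concern the primary endpoint.

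The primary objective in Section 3.1.1, also in the synopsis, is "to demonstrate a radiographic response rate of 15% or greater for the combination in a selected population".

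**The concern.** Read literally, Section 8.9 takes the design's alternative as the boundary of its null hypothesis. The error rates in Section 8.5 belong to the test against 2.5% and say nothing about a test against 15%. A statistician who programmes 8.9 as written would run a test with almost no chance of success at the rate used to size the trial.

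The practical risk is conflicting primary results. A trial that clears the Section 8.11 boundary would usually also report a non-significant primary test, and the plan does not say which of the two counts. Section 8.1 allows analysis changes without an amendment unless a significant feature changes, so the choice could end up being made after the data are seen.

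**Working it through.** **Inputs.** From Sections 8.5 and 8.11: p0 = 0.025, p1 = 0.150, n1 = 11 (stop at 0 responses), N = 37 (26 more patients in stage 2), success at 3 or more. From Section 8.9: a test of whether ORR exceeds 15%. Assumption: one-sided 5%, carried over from the 0.050 target in Section 8.5, because 8.9 gives no level.

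**1. Reproduce the stated design.** Let X1 ~ Bin(11, p) and X2 ~ Bin(26, p).

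- Early termination at 2.5%: 0.975^11 = 0.757.
- Expected sample size: 11 + (1 − 0.7569) × 26 = 17.32.
- P(declare success) = Σ over x ≥ 1 of P(X1 = x) × P(X2 ≥ 3 − x).
- At p = 0.025: 0.2135 × 0.1371 + 0.0274 × 0.4823 + 0.0022 = 0.0447 (stated 0.045).
- At p = 0.15: 0.3248 × 0.9183 + 0.2866 × 0.9854 + 0.2212 = 0.802, so the type II error is 0.198 (stated 0.198).

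Every stated figure reproduces, and a grid search confirms that this is the optimal design. The fault lies in the hypothesis in 8.9, not in the design.

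**2. Critical value of the Section 8.9 test.** Upper tail of Bin(37, 0.15):

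| Responses | Rate | One-sided p against 15% |
|---|---|---|
| 3 | 8.1% | 0.931 |
| 6 | 16.2% | 0.487 |
| 9 | 24.3% | 0.092 |
| 10 | 27.0% | 0.042 |

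The test needs at least 10 responses. At the design's own success boundary of 3 of 37 the p-value is 0.93.

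**3. Chance of success under 8.9.** At a true rate of 15%, P(X ≥ 10) = 0.0419 in one stage and 0.0414 through the two-stage path. It fails with probability 1 − 0.0414 = 0.959. Through the two-stage path, power is 0.446 at a true rate of 25%, 0.707 at 30% and 0.881 at 35%.

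**4. How often the two rules disagree.** They disagree when stage 1 is passed and the total is 3 to 9. At a true 15% rate this has probability 0.8019 − 0.0414 = 0.7606.

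**5. Sensitivity to what 8.9 leaves open** (one-stage failure probability at a true 15% rate):

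| Setting | Responses needed | Probability of failure |
|---|---|---|
| N = 37, one-sided 10% | 9 | 0.908 |
| N = 37, one-sided 5% | 10 | 0.958 |
| N = 37, one-sided 2.5% | 11 | 0.983 |
| N = 35 to 40, one-sided 5% | 10 or 11 | 0.951 to 0.975 |

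**6. Is it enough to replace 15% by 2.5%?** No. A one-stage exact test of 3 of 37 against 2.5% gives p = 0.065, and 4 of 37 gives p = 0.013. A one-stage test would therefore reject a result that the design accepts. Type I error at the 3-response boundary is 0.0447 only when the stage 1 stop is counted.

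**The case against.** The strongest reply is that this is loose drafting. The sentence in 8.9 may simply name the design's alternative: it never calls 15% the null, and it attaches no decision to the test. The two-stage rule is stated three times, in the synopsis, 8.5 and 8.11, and the synopsis methods contain no test against 15%. On that reading the decision rule is clear and one sentence needs tidying. A slip is quite possible, but the text still specifies the wrong test, and nothing in the plan subordinates it to the two-stage rule.

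A second point is that the 96% is close to automatic. Any valid test of ORR at most 15%, run when the true rate is exactly 15%, fails at least 1 − α of the time, and the 5% level is borrowed from Section 8.5. Both observations are correct. The figure shows where the boundary was placed; it is not a separate loss of power. The 0.76 probability of conflicting answers is the more informative number.

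Third, the objective in 3.1.1 names no test, and its 15% matches the alternative, so it is weaker evidence than 8.9. That is fair. The difficulty there is the promise to demonstrate 15%, which a success at 3 of 37 (8.1%) cannot support.

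Finally, the 95% exact interval that 8.9 will report at 3 of 37 runs from 1.7% to 21.9% and includes 2.5%. A positive result at the boundary therefore rejects 2.5% under the two-stage rule without excluding it from that interval. This stands, and the fix has to allow for it.

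**Conclusion.** The concern holds, and the text must be corrected. Section 8.9 contradicts Sections 8.5 and 8.11 on the primary hypothesis, and no other section reconciles them. With 37 patients and a one-sided 5% level, the 8.9 test needs 10 responses where the design needs 3. It succeeds with probability 0.042 at the target rate, where the design has 0.802, and at that rate the two rules disagree with probability 0.76. The significance level is an assumption taken from the design's own target, but the conclusion does not depend on it: failure stays between 91% and 98% for one-sided levels from 10% to 2.5%. The sample size, stopping rule and stated error rates are sound.

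**What to change.** - **Section 8.9.** Replace the test sentence with text to this effect: the primary analysis is the two-stage rule of Sections 8.5 and 8.11; the null hypothesis that ORR is at most 2.5% is rejected if at least 1 of the first 11 and at least 3 of all 37 evaluable patients have a confirmed response.
- **p-value and interval.** State that any reported p-value will account for the two stages. Also say either that the confidence interval will do so or that the ordinary exact interval is descriptive and may include 2.5% at the boundary.
- **Section 3.1.1 and synopsis.** Reword the primary objective as testing whether ORR exceeds 2.5%, with 15% as the target rate the design is powered to detect.
- **Number analysed.** Say explicitly that the decision is made on 37 evaluable patients, with enrolment of up to 40 serving to reach that number. Applying the 3-response boundary to 40 patients would give a type I error of 0.051, just over the 0.050 target.

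The cost is a wording amendment, with no change to sample size, conduct or stopping rule. The claim becomes more modest: a positive trial rejects 2.5% under the two-stage rule and does not establish 15%.
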